4.4. End of Study Definition

End of Study Definition

The end of the study is defined as the last follow-up assessment for the last participant in the study (see Section 4.1.3 for further details). The final data from the study site will be sent to the sponsor (or designee) after completion of the final participant visit at that study site, in the time frame specified in the Clinical Trial Agreement.

Study Completion Definition

A participant will be considered to have completed the main study if he or she has completed assessments through Week 52 and the 12-week safety follow-up visit or has completed the assessments through Week 52 and enters the LTE. A participant will be considered to have completed the full study if he or she has completed assessments through Week 152 and the 12-week safety follow-up visit.

5. STUDY POPULATION

Screening for eligible participants will be performed within 8 weeks before administration of the study intervention. Refer to Section 5.4, Screen Failures for conditions under which the repeat of any screening procedures are allowed.

The inclusion and exclusion criteria for enrolling participants in this study are described below. If there is a question about these criteria, the investigator must consult with the appropriate sponsor representative and resolve any issues before enrolling a participant in the study. Waivers are not allowed. The inclusion and exclusion criteria will be adjudicated prior to enrollment. The

adjudicated assessment by the sponsor or designee will be the final determinant for allowing enrollment.

For a discussion of the statistical considerations of participant selection, refer to Section 9.2, Sample Size Determination.

5.1. Main Study Inclusion Criteria

Each potential participant must satisfy all of the following criteria to be enrolled in the study:

1. Male or female (according to their reproductive organs and functions assigned by chromosomal complement).
2. 18 to 75 years of age, inclusive.
3. Meets classification criteria for SLE by the 2019 European League Against Rheumatism (EULAR)/ACR.
4. Criterion modified per Amendment 3.
 - 4.1. Kidney biopsy documentation of active ISN/RPS proliferative nephritis: Class III-IV (with or without class V membranous nephritis) within the last 6 months prior to screening or performed during screening.

Concomitant or previous medical therapies received

5. Criterion modified per Amendment 3.
 - 5.1. Must have received MMF or MPA for at least 8 weeks at the time of randomization, and currently receiving MMF at a dose of ≤ 3 g/day or MPA at dose of ≤ 2.2 g/day.

Note: Screening may be extended by up to 4 additional weeks for participants who start MMF/MPA at or near (within 2 weeks before) the beginning of screening to allow for repeat of laboratory entry criteria after 8 weeks of MMF/MPA treatment.
6. Criterion modified per Amendment 3.
 - 6.1. At screening and randomization, must be receiving oral glucocorticoids at minimum prednisone equivalent dose of 10 mg/day and maximum 1 mg/kg/day or ≤ 60 mg/day, whichever is lower. Treated for ≥ 6 weeks with stable dosing ≥ 2 weeks before randomization.
7. If receiving angiotensin-converting enzyme (ACE) inhibitor/angiotensin II receptor blockers (ARB), a stable dose for at least 2 weeks prior to randomization.
8. If using antimalarials, must have been treated for ≥ 12 weeks, and with stable dosing for ≥ 6 weeks at time of randomization. See [Table 5](#) for permitted dosing levels.

Screening laboratory tests

9. Criterion modified per Amendment 3.
 - 9.1. Positive antinuclear antibody (ANA; $\geq 1:80$ titer by central laboratory test) or anti-dsDNA antibodies (≥ 30 IU/mL by central laboratory test) detected at screening.
10. UPCR ≥ 1.0 mg/mg assessed on 2 first morning urine void specimens during screening. Note: These 2 specimens do not need to be on consecutive days, however, 2 samples must be tested with UPCR ≥ 1.0 mg/mg in a row. The UPCR requirement must be met after at least 8 weeks of MMF/MPA treatment, and after stable glucocorticoid dosing is achieved at the dose intended at time of randomization.

Tuberculosis: The participant is considered eligible according to the following TB screening criteria in Inclusion #11 to 14:

11. Has no history of latent or active TB before screening. An exception is made for participants who have a history of latent TB AND satisfy one of the following criteria:
 - a. are currently receiving treatment for latent TB

OR

 - b. will initiate treatment for latent TB before the first dose of study intervention

OR

 - c. have documentation of having completed appropriate treatment for latent TB within 5 years before the first dose of study intervention. It is the responsibility of the investigator to verify the adequacy of previous anti-tuberculous treatment and provide appropriate documentation. Patients with a history and documentation of having completed appropriate treatment for latent TB more than 5 years before the first dose of study intervention are not eligible.
12. Has no signs or symptoms suggestive of active TB based on medical history and/or physical examination.
13. Has had no recent close contact with a person with active TB or, if there has been such contact, will be referred to a physician specializing in TB to undergo additional evaluation and, if warranted, receive appropriate treatment for latent TB before the first dose of study intervention.
14. Within 8 weeks prior to the first dose of study intervention, have a negative QuantiFERON-TB[®] test result, or have a newly identified positive QuantiFERON-TB[®] test in which active TB has been ruled out and for which appropriate treatment for latent TB has been initiated prior to the first dose of study intervention (see Section 8.2.11). Indeterminate or borderline results should have the test repeated as described in Section 8.2.11.

Note: A negative tuberculin skin test result (see Appendix 3 [Section 10.3]) is additionally required if the QuantiFERON-TB[®] test is not approved/registered in the country in which this protocol is being conducted. In Ukraine, while the QuantiFERON-TB[®] test is not approved/registered, it is acceptable, and an additional tuberculin skin test is not required. The QuantiFERON-TB[®] test and the tuberculin

skin test are not required at screening for participants with a history of latent TB, if active TB has been ruled out, and if appropriate treatment has been initiated/completed as described above in Inclusion Criterion #11.

Has a chest radiograph (both posterior-anterior and lateral views, or per country regulations where applicable), taken within 12 weeks prior to randomization and read by a qualified radiologist (or pulmonologist in accordance with local regulations), with no evidence of current, active TB or old, inactive TB. A chest computed tomography (CT) scan is also acceptable if obtained instead of a chest radiograph outside of the protocol.

Contraception

Contraceptive (birth control) use by men or women should be consistent with local regulations regarding the acceptable methods of contraception for those participating in clinical studies.

Typical use failure rates may differ from those when used consistently and correctly. Use should be consistent with local regulations regarding the use of contraceptive methods for participants in clinical studies.

15. A woman of childbearing potential must have a negative urine pregnancy test at screening and at Week 0.
16. A woman must agree not to donate eggs (ova, oocytes) for the purposes of assisted reproduction during the study and for 12 weeks after the last dose of study intervention.
17. Criterion modified per Amendment 2.

17.1. Before randomization, a woman must be (as defined in Appendix 5 [Section 10.5], Contraceptive and Barrier Guidance and Collection of Pregnancy Information):

- a. Not of childbearing potential

OR

- b. Of childbearing potential and:

- If heterosexually active, practicing a highly effective method of contraception (failure rate of <1% per year when used consistently and correctly) and agrees to remain on a highly effective method while receiving study intervention and until 12 weeks after last dose (ie, the end of relevant systemic exposure). Examples of highly effective methods of contraception are located in Appendix 5 (Section 10.5), Contraceptive and Barrier Guidance and Collection of Pregnancy Information; however, the method selected must meet local/regional regulations/guidelines for highly effective contraception.
- If using oral hormonal contraceptives for birth control and receiving MMF/MPA, a woman must, in addition to the oral hormonal contraceptive, utilize a barrier method of birth control (eg, either an occlusive cap [diaphragm or cervical/vault caps] plus spermicidal

foam/gel/film/cream/suppository if available in their locale) or their partner must agree to use a condom with spermicidal foam/gel/film/cream/suppository if available in their locale, during the study and for at least 30 days after receiving the last administration of study intervention.

Note: If a participant's childbearing potential changes after start of the study (eg, a premenarchal woman experiences menarche) or the risk of pregnancy changes (eg, a woman who is not heterosexually active becomes active), a woman must begin using a highly effective method of contraception, as described above.

18. A man who is sexually active with a woman of childbearing potential and who has not had a vasectomy must agree to use a barrier method of birth control, eg, either condom with spermicidal foam/gel/film/cream/suppository or partner with occlusive cap (diaphragm or cervical/vault caps) with spermicidal foam/gel/film/cream/suppository.
19. A male participant must agree not to donate sperm for the purpose of reproduction during the study and for a minimum of 12 weeks after receiving the last dose of study intervention.

General

20. Must sign an ICF indicating that he or she understands the purpose of, and procedures required for, the study and is willing to participate in the study. (In regions where the legal age of consent is older than 18 years, those under the legal age, must obtain signed informed consent from both the participant and his or her legally acceptable representative.)
21. Must sign a separate ICF if he or she agrees to provide optional DNA samples for research where local regulations permit. In regions where the legal age of consent is older than 18 years, those under the legal age, must obtain signed informed consent from both the participant and his or her legally acceptable representative.
Refusal to give consent for the optional DNA samples does not exclude a participant from participation in the study.
22. Must be willing and able to adhere to all specified requirements, including but not limited to completion of the required assessments, adherence to the visit schedule, and compliance with the lifestyle restrictions as specified in this protocol.
23. Must be able to read and write.

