5.3. Lifestyle Considerations

Potential participants must be willing and able to adhere to the following lifestyle restrictions during the course of the study including the LTE to be eligible for participation:

1. Refer to Section 6.5, Concomitant Therapy for details regarding prohibited and restricted therapy during the study.
2. Agree to follow all requirements that must be met during the study as noted in the inclusion and exclusion criteria (eg, contraceptive requirements).
3. Participants must follow contraceptive measures as outlined in Section 5.1, Inclusion Criteria. Participants should continue using these contraceptive measures for 12 weeks after last dose of study intervention.
4. Must agree not to receive a live virus or live bacterial vaccination during the study and for 12 weeks after receiving the last dose of study intervention.
5. Must agree not to receive a BCG vaccination during the study and for 12 months after receiving the last dose of study intervention.
6. Participants who require treatment for latent TB must complete the appropriate course of TB therapy as described in Section 5.1, Inclusion Criteria.
7. Must not receive guselkumab outside of this protocol or participate in any other clinical study with an investigational agent while in this study and must terminate study participation if they do. A participant who intends to participate in any other clinical study with an investigational agent should complete the appropriate visit(s) as described in Section 1.3 before he or she terminates study participation.
8. Agree to avoid excess exposure to natural or artificial (tanning beds, phototherapy, etc) sunlight. In addition, it is advised that subjects maintain their typical use of sun protective measures (such as a hat, sunglasses, protective clothing, sunscreen). The time period for this requirement is from the start of screening until the last dose of study agent has been received.

9. Participants who are entering the LTE and self-administering the study intervention at home must be willing and able to complete a diary card to document clinical symptoms, AEs, etc.

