Participants must undergo testing for TB and their medical history assessment must include specific questions about a history of TB or known occupational or other personal exposure to individuals with active TB (Section 8.2.11 and Appendix 3 [Section 10.3]).

Women of childbearing potential must have a negative urine pregnancy test result at screening and at each visit and before any study intervention administration. Participants who are women of childbearing potential must be reminded that they are required to use a highly effective method of contraception during the study (as described in Section 5.1, Inclusion Criterion 17 and Appendix 5 [Section 10.5]) and must continue taking such precautions for 12 weeks after receiving the last dose of study intervention. The method(s) of contraception used by each participant must be documented.

All screening evaluations establishing participant eligibility will be performed and reviewed by the investigator before a participant can be randomized. Participants must have received approval for study randomization following adjudication of inclusion and exclusion criteria.

A kidney biopsy is required if one has not been done within the last 6 months prior to screening to confirm Class III/IV (ISN/RPS) proliferative nephritis (with or without class V [ISN/RPS] membranous nephritis). A de-identified copy of the pathology report will be required to be provided, tissue samples will be requested (where applicable or where local regulations permit) for all kidney biopsies during screening or within the last 6 months. If the participant is undergoing a kidney biopsy during screening, the participant should meet all other eligibility criteria prior to a biopsy being performed.

Documentation (historical or local laboratory testing) of unequivocally positive values (as defined in the laboratory's reference range) should be provided for the following: ANA (eg, ANA by human epithelial type 2 cells [HEp-2] titer, ANA by enzyme-linked immunosorbent assay [ELISA]), or anti-dsDNA (eg, anti-dsDNA by Farr assay or ELISA), or anti-Smith. To establish participant eligibility, these results must be confirmed through central laboratory testing.

Blood Sample Collection

During the main study, the total blood volume to be collected from each participant will be approximately 720 mL for those at sites collecting biomarkers, and approximately 380 mL for

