
 • Periodic abstinence (calendar, symptothermal, post-ovulation methods)

 • Withdrawal (coitus-interruptus)

 • Spermicides alone

 • Lactational amenorrhea method (LAM)

a) Typical use failure rates may differ from those when used consistently and correctly. Use should be consistent with local regulations regarding the use of contraceptive methods for participants in clinical studies.
 
b) Hormonal contraception may be susceptible to interaction with the study intervention or concomitant medications (eg, mycophenolate mofetil [MMF]/mycophenolic acid [MPA] in combination with oral hormonal contraceptives), which may reduce the efficacy of the contraceptive method. In female participants who are of childbearing potential and are receiving MMF/MPA, a barrier contraceptive method should be used concurrently with oral hormonal contraception methods (Section 5.1, Inclusion Criterion #17).

c) Male condom and female condom should not be used together (due to risk of failure with friction).

Pregnancy During the Study

All initial reports of pregnancy in female participants or partners of male participants must be reported to the sponsor or designee by the study-site personnel within 24 hours of their knowledge of the event using the appropriate pregnancy notification form. Abnormal pregnancy outcomes (eg, spontaneous abortion, fetal death, stillbirth, congenital anomalies, ectopic pregnancy) are considered serious adverse events (SAEs) and must be reported using the Serious Adverse Event Form. Any participant who becomes pregnant during the study must discontinue further study intervention.

Follow-up information regarding the outcome of the pregnancy and any postnatal sequelae in the infant will be required.

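### Criterion 17.1b gives the barrier added to oral contraceptives a 30-day post-dose minimum, while the rest of the protocol supports 12 weeks

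*Protocol*

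**What the plan says.** All locations are in the Protocol.

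- **Section 5.1, criterion 17.1b, second bullet.** A woman on oral hormonal contraception and MMF/MPA must add a barrier, or her partner must use one, "during the study and for at least 30 days after receiving the last administration of study intervention".
- **Section 5.1, criterion 17.1b, first bullet.** For a heterosexually active woman of childbearing potential, the commitment is: "remain on a highly effective method while receiving study intervention and until 12 weeks after last dose (ie, the end of relevant systemic exposure").
- **Section 5.3, item 3.** After pointing to the contraceptive measures of Section 5.1, it adds: "Participants should continue using these contraceptive measures for 12 weeks after last dose of study intervention".
- **Section 8, Screening Phase.** Citing criterion 17 and Appendix 5, it says women of childbearing potential "must continue taking such precautions for 12 weeks after receiving the last dose of study intervention".
- **Appendix 5, note b.** Hormonal contraception may interact with concomitant drugs, with MMF/MPA plus an oral contraceptive as the example, "which may reduce the efficacy of the contraceptive method". For women on MMF/MPA, "a barrier contraceptive method should be used concurrently with oral hormonal contraception methods". No end date is given.
- **Section 5.1, criterion 22.** Participants must be willing and able to meet the study requirements, including "compliance with the lifestyle restrictions as specified in this protocol". The lifestyle restrictions are those of Section 5.3.

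**The concern.** The barrier exists because MMF/MPA may weaken the oral contraceptive. MMF/MPA is required background therapy, so this applies to every oral-contraceptive user in the trial. If the oral method has to be effective for 12 weeks after the last dose, the barrier that supports it should run just as long. The second bullet instead gives a minimum of 30 days, and it is the only sentence in the protocol that states a post-dose period specifically for this barrier.

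The stake is participant safety. A site working from this bullet alone could give day 30 as the stop date to a woman who then leaves the study while still taking MMF/MPA. From day 31 to day 84 she would rely on an oral method that the protocol itself describes as possibly weakened.

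**Working it through.** The protocol gives no calculation to reproduce. The check compares the stated periods and then sizes the gap.

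**Stated post-dose periods**

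| Location | Measure | Period after last dose |
|---|---|---|
| Criterion 17.1b, second bullet | Barrier added to oral contraceptive on MMF/MPA | At least 30 days |
| Criterion 17.1b, first bullet | Highly effective method | 12 weeks |
| Section 5.3 item 3 | Contraceptive measures of Section 5.1 | 12 weeks |
| Section 8 | Precautions, citing criterion 17 and Appendix 5 | 12 weeks |
| Criterion 16 | Egg donation | 12 weeks |
| Criterion 19 | Sperm donation | Minimum of 12 weeks |
| Exclusion 49 | Planned pregnancy | 12 weeks |

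The 30-day figure stands alone. Criterion 19 shows that a post-dose period worded as a floor is set at 12 weeks elsewhere: "during the study and for a minimum of 12 weeks after receiving the last dose of study intervention".

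**Could 30 days be a deliberate, shorter period for the mycophenolate interaction?** The text does not support that. The 30 days run from the last study intervention, not from the last MMF/MPA dose, so they do not follow the interaction. The amendment history in Appendix 13 (Amendment 2) explains why the barrier was added, but not its duration.

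**Who could be affected.** The requirement covers the whole time in the study as well as the 30 days. Under early termination, Table 1 footnote c schedules a final efficacy visit about 4 weeks after the last dose and a safety visit at about 12 weeks. A woman who stays to the safety visit is covered throughout. Section 7.2 does not require participants who terminate participation to return, and it rules out further assessments after withdrawal of consent. Footnote d does ask those who stop drug and do not wish to continue to come back at 12 weeks.

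**Size of the gap if the bullet is read alone.** Let t be the days from last dose to leaving the study.

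- 12 weeks × 7 = 84 days.
- Shortfall(t) = 84 − max(t, 30) for t < 84, and 0 for t ≥ 84.
- t = 28 (leaves after the final efficacy visit, 4 × 7): 84 − 30 = 54 days, and 54/84 = 64%. This is the maximum and applies to any t up to 30.
- t = 56: 84 − 56 = 28 days.
- t = 84: 0.

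If the bullet is read together with Sections 5.3 and 8, the shortfall is 0 for every t.

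**The case against.** The strongest reply is that the protocol already covers this. Thirty days is a floor, so 12 weeks of barrier use complies with it. Section 5.3, made binding through criterion 22, extends the Section 5.1 measures to 12 weeks. The wording also covers anyone still in the study at the 12-week safety visit. All of this stands, and it is why the point is minor.

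A second reply is that the first bullet and Section 8 speak of a highly effective method, while Appendix 5 does not class barriers as highly effective on their own. On a literal reading, only Section 5.3 plainly reaches the barrier. This has some force for the first bullet. It has less for Section 8, which refers to criterion 17 and Appendix 5 as a whole, and note b ties the barrier to the oral method that must last 12 weeks.

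A third reply is that Amendment 2 added the text because of mycophenolate label changes, so it may address a risk separate from guselkumab exposure. Whether 30 days came from a label cannot be checked here. The choice of clock, the last study intervention, counts against that reading.

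Finally, the residual case is narrow: an oral-contraceptive user who leaves before day 84, at a site that reads one bullet alone. Screening of new participants has also stopped. Both points are fair. They limit the reach but do not make the texts agree.

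**Conclusion.** The concern holds, at minor severity. The second bullet of criterion 17.1b states a shorter minimum than Section 5.3 and Section 8 support, and shorter than the 12 weeks for which the oral method must remain effective. No reason is given.

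The gap is at most 54 of 84 days, and only if the bullet is read in isolation and the woman leaves before the 12-week visit. The group is women of childbearing potential on oral hormonal contraception with MMF/MPA, within a study of fewer than 60 participants. The documents give no count, and it may be zero. What the consent form told these women cannot be checked from the documents. The conclusion rests on reading the reference in Section 5.3 to the Section 5.1 measures as including the added barrier, which is its plain meaning. No endpoint, analysis population or statistical result depends on it.

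**What to change.** In the second bullet of criterion 17.1b, change the post-dose minimum from 30 days to 12 weeks, and give the same end date in Appendix 5 note b.

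Send sites a short Protocol Clarification Communication now. Section 10.9.1 allows one where wording is unclear and study conduct does not change. That condition is met because 12 weeks already applies when the protocol is read whole. The same section requires the content to be carried into any later amendment. Ask sites to confirm the 12-week end date with enrolled women on oral contraceptives no later than the final efficacy visit, which at about 4 weeks falls just before day 30.

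The cost is one site notice and two wording edits. In practice, a few early leavers who had been told 30 days would use a barrier for up to 54 days longer. If the consent form also says 30 days, its correction would need ethics committee review under Section 10.9.1. That cost cannot be judged from the documents. No procedure, endpoint or analysis changes.
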